4.5.6 Physical and Neurological Exams

The full physical examination will include head, ears, eyes, nose, mouth, skin, heart and lung, lymph nodes, and gastrointestinal, musculoskeletal, and neurological systems. The brief physical examination will be focused on general appearance and respiratory and cardiovascular systems, as well as on subject-reported symptoms.

The full neurological examination includes observation for cerebellar (intention) tremor and noncerebellar (e.g., resting or positional) tremor, nose-finger, heel-shin, Romberg, tandem walk, normal walk/gait, positional nystagmus, gaze-evoked nystagmus, reflexes, muscle strength, cranial nerves, and sensory function of the upper and lower extremities. The neurological examination will be performed by a physician or the equivalent.

The brief neurological examination will include an assessment of motor and sensory function, cranial nerves, reflexes, noncerebellar tremors (e.g., resting or positional), and cerebellar function. The assessment of cerebellar function will be complemented by the SARA. The brief neurological examinations will be conducted by a physician or the equivalent.

The summary table for Physical and Neurological Exams will include number of subjects who are assessed as Normal, Abnormal (Not clinically significant), Abnormal (clinically significant), and Not done/Missing for each function.

Table 10: Visit windows for Brief Physical and Neurological Examination

Analysis visit	Target visit day	Analysis visit window
Baseline	1	Most recent non-missing pre-dose value
Week 1	8	[2, 10]
Week 2	15	[11, 28]
Week 6	43	[29, 63]
Safety follow-up	Safety follow-up	[64, the end of study]

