¹¹ Whenever possible, screening laboratory values should be taken following at least a 4-hour fast.

¹² The screening efficacy assessments should, if possible, be completed in the following order: MCCB,

[REDACTED], CGI-S. The MCCB, [REDACTED] should preferably be completed during a single screening day; subjects can take breaks between assessments. If the rater determines that MCCB and additional cognitive assessments cannot be completed the same day, such assessments can be continued the next day. However, the [REDACTED] assessments must be administered on the same day as their respective immediate recall assessments (contained in the MCCB). See Study Reference Manual for additional details.

¹³ A smart phone application will be used to collect study data (e.g., compliance check). Subjects may use their own phone for phone applications, or a phone can be provided for the duration of the study.

¹⁴ The 7-day Placebo Lead-In evaluation may begin any time after eligibility has been established based on Screening assessments, provided that the Placebo Lead-In is completed no earlier than 3 days prior to the Baseline/Day 1 Visit.

CONFIDENTIAL

The information contained herein may not be used, disclosed, or published without the written consent of Biogen MA Inc.

Table 4: Schedule of Activities – Placebo-Controlled Treatment and Safety Follow-Up

Study Phase:	Baseline	Treatment							SFU
Protocol Activity	Day 1 ¹	Week 1/ Day 8 ²	Week 2/ Day 15 ^{1, 2}	Week 4/ Day 29 ²	Week 6/ Day 43 ^{1, 2}	Week 8/ Day 57 ²	Week 10/ Day 71 ²	Week 12/ Day 85 ^{1, 2} /ET ³	14 Days After Last Dose ²
Inclusion/Exclusion Criteria Review	X ⁴								
Randomization	X								
Medical, Neurological, Psychiatric, and Medication History	X								
C-SSRS ^{5, 6}	X	X	X	X	X	X	X	X	X
Study Guidelines Review ⁷	X	X	X	X	X	X	X	X	
Contraception Check ⁸	X	X	X	X	X	X	X	X	
Concomitant Psychiatric Medication Check	X	X	X	X	X	X	X	X	X
Weight ⁶	X		X	X	X	X		X	
Full Physical and Neurological Examination ⁶								X	
Brief Physical and Neurological Examination ⁶	X ^{9, 10}	X ¹⁰	X		X				X
SARA ⁶	X ^{9, 10}	X ¹⁰	X		X			X	X
12-Lead ECG ⁶	X ¹⁰	X ¹⁰	X	X	X	X		X	
12-Lead ECG, Triplicate ⁶	X								

CONFIDENTIAL

The information contained herein may not be used, disclosed, or published without the written consent of Biogen MA Inc.

Study Phase:	Baseline	Treatment								SFU

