¹ If needed, cognitive behavioral assessments may be completed over 2 consecutive working days for feasibility and subject comfort. The following efficacy assessments should, whenever possible, be completed in the following order: MCCB, [REDACTED] SCI-PANSS, UPSA-Bi, SCoRS, CGI-S, CGI-I.

² The visit window is ± 3 calendar days relative to baseline. The total time between visits is not to exceed 10 calendar days (for Week 2) or 17 calendar days (for all other visits).

³ Week 12 (Day 85/ET) assessments should be completed in the event of early subject withdrawal/early termination (ET).

⁴ The site will review all Screening Visit assessments against the inclusion/exclusion criteria, assess for any changes from screening, and reconfirm eligibility prior to randomization.

⁵ C-SSRS “Since Last Visit” evaluation.

⁶ The following safety assessments should, whenever possible, be completed in this order: C-SSRS, concomitant medications, weight, physical examination, neurological examination, SARA, 12-lead ECG, vital signs, urine drug and alcohol screening, blood/urine specimens.

⁷ See Section 8.3 and the Study Reference Manual for additional information.

⁸ All women of childbearing potential and all men must practice effective contraception during the study. After their last dose of study treatment, men and women must continue with contraception for at least 30 days.

⁹ To be performed predose for all study sites. For Japanese study sites, see Footnote 10 for additional instructions.

¹⁰ **For Japanese study sites only** (items designated with Footnote 10 are for Japanese sites only unless otherwise specified):

- On Day 1, in addition to baseline assessments, a [REDACTED] will be collected (see Table 5 for timing) and additional safety evaluations (AE recording, 12-lead ECG, brief neurological examination, and SARA) will be performed 2-hours postdose. Should any abnormal findings arise during these evaluations, an additional [REDACTED] will be collected. Dosing will be performed under medical supervision, and observation may be extended at the Investigator’s discretion prior to discharge from the site, if necessary, including an overnight stay.
- On Day 8, a [REDACTED] will be collected (see Table 5 for timing), and additional safety assessments 2-hours postdose (AE recording, 12-lead ECG, brief neurological examination, and SARA) will be performed.

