7. STUDY DESIGN

This is a Phase 2, randomized, double-blind, placebo-controlled, parallel-group study to evaluate the safety, tolerability, and efficacy of BIIB104 in subjects with CIAS. Approximately 219 male and female subjects with stable schizophrenia from age 18 to 55 years, inclusive, will be recruited. Dosing with BIIB104 0.15 mg BID and 0.5 mg BID versus placebo will be evaluated over a treatment phase of 12 weeks. The study will be conducted at approximately 80 sites globally.

The study includes a screening phase, a placebo lead-in phase, a randomized treatment phase, and a safety follow-up (SFU) phase to begin after the last dose of study treatment. The primary analysis will be conducted after 12 weeks of placebo-controlled treatment.

[figure not shown]
Screening evaluation will occur up to 35 days prior to randomization. Once eligibility has been established, a 7-day Placebo Lead-In evaluation will be conducted to assess the subject's ability to comply with dosing requirements; this evaluation must be completed no earlier than 3 days prior to the Baseline/Day 1 Visit. After Sponsor reconfirmation of eligibility and completion of baseline measurements at the Baseline/Day 1 Visit, subjects will be randomized in a 1:1:1 ratio to receive BIIB104 0.5 mg, BIIB104 0.15 mg, or placebo (planned for 73 subjects per treatment group). The randomization will be stratified by region. Subjects will be dosed at approximately 12-hour intervals for approximately 12 weeks. Total duration of subject participation will be approximately 19 weeks from screening to final follow-up visit.

See [Figure 1](#) for a schematic presentation of the study design.

CONFIDENTIAL

The information contained herein may not be used, disclosed, or published without the written consent of
Biogen MA Inc.

Figure 1: Study 263CS201 Schematic

N = number of subjects; MCCB = MATRICS Consensus Cognitive Battery; BID = twice daily.

*Note: The Placebo Lead-In evaluation may begin any time after eligibility has been established based on screening assessments, provided that the Placebo Lead-In is completed no earlier than 3 days prior to the Baseline/Day 1 Visit.

CONFIDENTIAL

The information contained herein may not be used, disclosed, or published without the written consent of Biogen MA Inc.

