10. DISCONTINUATION OF STUDY TREATMENT AND WITHDRAWAL OF SUBJECTS FROM THE STUDY

10.1. Discontinuation of Study Treatment

A subject must permanently discontinue study treatment for any of the following reasons:

- The subject becomes pregnant. Study treatment must be discontinued immediately, and the pregnancy must be reported according to the instructions in Section [15.4.1](#).
- Any seizure event. If a seizure event is suspected, the subject must discontinue study treatment and be referred to a neurologist for appropriate follow-up (see Section [7.3](#)). An effort should be made to collect a [REDACTED] as soon as possible after the event.
- The subject withdraws consent.
- The subject experiences a medical emergency that necessitates permanent discontinuation of study treatment or unblinding of the subject's treatment assignment.
- The subject experiences an AE requiring continued treatment that meets exclusionary criteria.
- The subject has confirmed ALT or AST $>5 \times$ ULN, or confirmed ALT or AST $>3 \times$ ULN and bilirubin $>2 \times$ ULN.
- Depending on the specifics of the subject's C-SSRS as assessed by the Investigator, subjects must have their suicidality managed appropriately by clinicians and must discontinue from the treatment.
- At the discretion of the Investigator, for medical reasons.
- At the discretion of the Investigator or the Sponsor, for noncompliance with the terms of the protocol.
- The primary reason for discontinuation of study treatment must be recorded in the subject's case report form (CRF).

All subjects who discontinue study treatment prematurely will be asked to remain in the study and continue all protocol-specified visits and procedures. At a minimum, these visits should include assessment of AEs/SAEs and concomitant medications and key clinical assessments. Subjects who discontinue study treatment prematurely will also be asked to return to the study site for an SFU Visit 14 days after receiving the last dose of study treatment.

CONFIDENTIAL

The information contained herein may not be used, disclosed, or published without the written consent of Biogen MA Inc.

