4.5.3.1 Quantitative Analyses

Hematology, serum chemistry, and urinalysis will be summarized by treatment group and visit. Descriptive statistics will be presented at each visit by treatment group, including number of subjects, mean, standard deviation, median, 25%, 75% quartiles, minimum, and maximum values.

Changes from baseline in quantitative laboratory values will be summarized using descriptive statistics by treatment group and visit. Plots of mean values by visits will be presented for numeric laboratory parameters, except for mean corpuscular volume (MCV), mean corpuscular hemoglobin (MCH), and mean corpuscular hemoglobin concentration (MCHC).

Individual subject listings of clinical laboratory parameters at each visit will be provided. Values for hematology, serum chemistry, and urinalysis values outside the central laboratory reference ranges will be flagged on the individual subject data listings.

Visit windows for by visit summaries

For laboratory by visit summaries, the analysis visit is defined by visit windows in the table below. If there is more than 1 value in the same analysis visit window for a certain parameter for a subject, then the closest record to the target visit day will be used for the by visit analysis. If there are 2 values in the same analysis visit window with the same distance from the target visit day for a certain parameter for a subject, then the record with the later date will be used for the by visit analysis. If there are 2 values on the same day for a certain parameter for a subject, then the record with the later time will be used for the by visit analysis.

Table 6: Visit Windows for Laboratory

Analysis visit	Target visit day	Analysis visit window
Baseline	1	Most recent non-missing pre-dose value
Week 1	8	[2, 10]
Week 2	15	[11, 21]
Week 4	29	[22, 42]
Week 8	57	[43, 70]
Week 12	85	[71, one day before start of safety follow-up]
Safety follow-up	Safety follow-up	[start of safety follow up, the end of study]

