4.5.7 SARA

Descriptive statistics will be used to summarize SARA measurements at each visit for each treatment group. Individual subject listings of SARA at each timepoint will also be provided by treatment group.

Table 11: Visit windows for SARA

Analysis visit	Target visit day	Analysis visit window
Baseline	1	Most recent non-missing pre-dose value
Week 1	8	[2, 10]
Week 2	15	[11, 28]
Week 6	43	[29, 63]
Week 12	85	[64, one day before start day of safety follow-up]
Safety follow-up	Safety follow-up	[Start day of safety follow-up, the end of study]

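### SAP Table 10 starts safety follow-up at a fixed Day 64, so the follow-up brief exam of a subject who stops treatment by about Day 49 falls in the Week 2 or Week 6 window

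*SAP*

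**What the plan says.** SAP 4.5.6 plans a summary of physical and neurological exams as normal, abnormal (clinically significant or not) or not done, for each function. Table 10 maps brief exams to visits by study day: Week 1 [2, 10], Week 2 [11, 28], Week 6 [29, 63], and safety follow-up ["64, the end of study"]. Nothing in 4.5.6 lets the recorded visit name override the day window, and no rule covers two exams in one window.

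Protocol Section 7 describes "a safety follow-up (SFU) phase to begin after the last dose of study treatment". Under Protocol 10.1, subjects who stop treatment early are to "return to the study site for an SFU Visit 14 days after receiving the last dose of study treatment". In Protocol Table 4, the row "Brief Physical and Neurological Examination" is marked at Day 1, Day 8 (Japanese sites), Week 2, Week 6 and the follow-up visit. Week 12/ET has the full exam instead.

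Two other SAP tables cover the same follow-up visit. Table 11 (SARA) uses ["Start day of safety follow-up, the end of study"] and Table 6 (laboratory) uses ["start of safety follow up, the end of study"].

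**The concern.** The follow-up visit moves with the last dose, but the Table 10 boundary does not. For a completer the visit falls near Day 99 and is labelled correctly. For a subject who stops early enough, the exam is done before Day 64 and the only matching row is Week 2 or Week 6.

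Two things can then go wrong. The exam may be counted at a scheduled treatment visit, where a normal off-drug finding dilutes the row and a persisting abnormality loses its follow-up label. Or, if a scheduled exam in the same window is preferred, the follow-up exam disappears from the by-visit summary. The subjects affected are early stoppers, some of whom may have stopped for adverse events.

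**Working it through.** **Inputs.** Table 10 windows (SAP 4.5.6). Follow-up at last dose + 14 days (Protocol 10.1 and Table 4). Visit window: "The visit window is ± 3 calendar days relative to baseline" (Protocol Table 4, footnote 2), which I apply to follow-up as last dose + 11 to + 17; this is a reading, since the footnote refers to baseline. Drop-out 30%, 73 per group, 219 in total (Protocol 16.6).

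**The plan's own figure, used only for scale.** 51 / (1 − 0.30) = 72.9, rounded up to 73 per group; 3 × 73 = 219. A noncentral-t calculation with difference 3.5, SD 7 and two-sided 0.10 gives power 0.806 at 51 per group. Both figures reproduce.

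**Which row receives the follow-up exam.** Let L be the study day of the last dose; the exam is on Day L + 14.

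| Last dose L | Exam day | Table 10 row |
|---|---|---|
| 1-14 | 15-28 | Week 2 |
| 15-49 | 29-63 | Week 6 |
| 50-85 | 64-99 | Safety follow-up |

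At L + 11 the exam misses the follow-up row for L = 1-52; at L + 17, for L = 1-46.

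**Where Day 64 may come from.** (43 + 85) / 2 = 64 is the midpoint of Week 6 and Week 12, and in Table 11 that day opens the Week 12 row. The midpoint between Week 12 and a completer's follow-up is (85 + 99) / 2 = 92. This suggests a boundary carried over from a table with a Week 12 row, but the SAP does not say so.

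**Scale, under stated assumptions.** Take drop-out as stopping treatment, uniform over Days 1-84, with every drop-out attending follow-up at 14 days.
- Drop-outs: 0.30 × 219 = 65.7.
- In the Week 2 window: 65.7 × 14/84 = 11.0. In the Week 6 window: 65.7 × 35/84 = 27.4. Total: 65.7 × 49/84 = 38.3.
- With 20% drop-out: 0.20 × 219 × 49/84 = 25.6.
- With 30% drop-out and half of them attending: 38.3 / 2 = 19.2.

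**If a closest-to-target rule is borrowed** from SAP 4.5.3.1, 4.5.4 or 4.5.8, and the subject attends only follow-up after stopping:
- L = 1-14: no Day 15 exam was done, so the follow-up exam is tabulated as Week 2.
- L = 15-42: no Day 43 exam was done, so it is tabulated as Week 6.
- L = 43-49: the Day 43 exam is on target and the follow-up exam is 14 to 20 days off, so the follow-up exam is dropped.
- Tabulated in the wrong row: 65.7 × 42/84 = 32.9. Dropped: 65.7 × 7/84 = 5.5.

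For subjects who stop drug but keep attending, the scheduled exam would normally win, and the follow-up exam would usually be dropped rather than tabulated.

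**The case against.** The strongest reply is that this is one descriptive table. Protocol 16.4.2 lists adverse events, laboratory data, vital signs, SARA and C-SSRS for safety evaluation, not the neurological exam. Findings recorded as adverse events are captured through follow-up whatever window the exam falls in. No test, endpoint or stopping rule uses Table 10. All of that stands, and it limits the importance of the point.

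Four stronger readings are tempting and are not supported:

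- A reader might call the missing Week 12 row an error. Table 10 is titled for brief exams, and none is scheduled at Week 12/ET. Only an unscheduled brief exam on drug from Day 64 would be mislabelled, unless the table is also applied to full exams that it does not name.
- A reader might infer that the SARA and the exam from one follow-up visit must carry different labels. Table 11's Week 2 and Week 6 windows are not cut off at follow-up either, so an early follow-up SARA fits two rows, and no precedence is stated.
- A reader might say that clean on-treatment rows are being contaminated. The rows are named Week 2 and Week 6, and Protocol 10.1 asks subjects who stop drug to keep attending, so these rows hold some off-drug exams by design.
- A reader might take 38 as an expected count. It assumes full attendance, and subjects who withdraw consent or are lost to follow-up may never have the exam.

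None of this removes the mismatch between a fixed study day and a visit defined from the last dose.

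**Conclusion.** The point holds as a small, definite inconsistency. Read literally, Table 10 cannot label the follow-up brief exam correctly when the last dose is on or before about Day 49 (Day 46 to 52 with the visit window). That follows from the windows and the visit schedule alone.

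The count does rest on assumptions. With 30% drop-out, uniform stopping and full attendance it is at most about 38 of 219, of which about 33 would be tabulated in the wrong row under a closest-record rule. Lower attendance could reduce it greatly; stopping concentrated early would push it up. The consequence is confined to a by-visit safety summary.

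**What to change.** In SAP 4.5.6 and the related tables:

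1. Change the Table 10 safety follow-up row to the Table 11 form, ["Start day of safety follow-up, the end of study"].
2. State that every earlier window ends no later than the day before the subject's follow-up starts, and apply this to Tables 6 and 11 as well. Copying Table 11 without the cut-off is not enough: with a last dose on Day 40, the exam on Day 54 would fit both Week 6 and follow-up.
3. Define the start day as either the follow-up visit or the day after the last dose. The choice decides where later exams go for subjects who stop drug but stay in the study.
4. Add the closest-to-target rule, with its tie-break, as in the laboratory, vital sign and ECG sections.
5. Leave Table 10 without a Week 12 row for brief exams. If the full Week 12/ET exam is to be summarised by visit, give it its own row ending the day before follow-up starts.

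The cost is a few lines of SAP text and the matching programming. No new data are needed. With items 1 and 2 in place, no follow-up exam falls in a Week 2 or Week 6 window for any last-dose day.

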4.5.7 SARA

Descriptive statistics will be used to summarize SARA measurements at each visit for each treatment group. Individual subject listings of SARA at each timepoint will also be provided by treatment group.

Table 11: Visit windows for SARA

Analysis visit	Target visit day	Analysis visit window
Baseline	1	Most recent non-missing pre-dose value
Week 1	8	[2, 10]
Week 2	15	[11, 28]
Week 6	43	[29, 63]
Week 12	85	[64, one day before start day of safety follow-up]
Safety follow-up	Safety follow-up	[Start day of safety follow-up, the end of study]

4.5.8 Electrocardiogram (ECG)

The ECG data will be obtained directly from the 12-lead ECG traces. These data include the PR interval, QTcB interval, QTcF interval, QRS duration, and pulse rate. The ECG data will be listed by subject. Descriptive statistics will be used to summarize ECG measurements at each visit for each treatment group. In addition, a shift table of ECG interpretation results will be presented at each visit by treatment group. Individual subject listings of ECG parameters at each timepoint will also be provided by treatment group. Plots of mean QTcB and mean QTcF over time will be also presented.

Visit windows for by visit summaries

For ECG by visit summaries, the analysis visit should be defined using window in the table below. If there is more than 1 value in the same analysis visit window for a certain parameter for a subject, the closest record to the target visit day will be used for the by visit analysis. If there are 2 values in the same analysis visit window with the same distance from the target visit day for a certain parameter for a subject, then the record with the later date will be used for the by visit analysis.

Table 12: Visit windows for ECG

Analysis visit	Target visit day	Analysis visit window
Baseline	1	Most recent non-missing pre-dose value
Week 2	15	[2, 21]
Week 4	29	[22, 35]
Week 6	43	[36, 49]
Week 8	57	[50, 70]
Week 12	85	[71, EOS]

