14.1.6. Electrocardiogram

Triplet and single ECGs will be collected as specified in the Schedules of Activities (Section 5). Samples obtained outside the proposed sampling timepoints specified in will not be captured as a protocol deviation, as long as the exact time of the assessment is noted on the source document and data collection tool (e.g., CRF).

All scheduled ECGs should be performed after the subject has rested quietly for at least 10 minutes in a supine position. Triplet 12-lead ECGs will be obtained approximately 2 to 4 minutes apart; the average of the triplet ECG measurements collected before dosing on Day 1 will serve the subject's baseline QTc value. When the timing of these measurements coincides with a blood collection, the ECG should be obtained prior to the nominal time of the blood collection, blood pressure, and pulse rate.

To ensure safety of the subjects, a qualified individual at the study site will make comparisons to baseline measurements. If the QTc interval is increased by ≥ 45 msec from the baseline, or an absolute QTc value is ≥ 500 msec for any scheduled ECG, then 2 additional ECGs will be collected (approximately 2 to 4 minutes apart) to confirm the original measurement. If either of the QTc values from these repeated ECGs remains above the threshold value (≥ 45 msec above the baseline) or is ≥ 500 msec, then a single ECG must be repeated at least hourly until QTc values from 2 successive ECGs fall below the threshold value that triggered the repeat measurement.

If QTc values are >500 msec (or ≥ 45 msec above the baseline) for more than 4 hours (or sooner at the discretion of the Investigator), or if QTc intervals get progressively longer, the subject should undergo continuous ECG monitoring. A cardiologist should be consulted if QTc intervals do not return to <500 msec (or to <45 msec above the baseline) after 8 hours of monitoring (or sooner at the discretion of the Investigator).

In some cases, it may be appropriate to repeat abnormal ECGs to rule out improper lead placement as contributing to the ECG abnormality. It is important that leads are placed in the same positions each time in order to achieve precise ECG recordings. If a machine-read QTc value is prolonged, as defined above, repeat measurements may not be necessary if a qualified physician's interpretation determines that the QTc values are in the acceptable range.

CONFIDENTIAL

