4.5.3.2 Qualitative analysis

Clinically significant laboratories

Clinically significant laboratory data will be summarized using shift tables where appropriate. For each subject, the lab values in hematology, blood chemistry and urinalysis will be flagged as “low”, “normal”, or “high” relative to the normal ranges of the central laboratory, or as “unknown” if no result is available. The categorical value in urinalysis will be flagged as “positive” (or “high”), “negative” (or “normal”), or “unknown”.

For blood chemistry and serum chemistry, shifts tables from baseline to low/high post-baseline will be presented. Shift to low includes normal to low, high to low, and unknown to low. Shift to high includes normal to high, low to high, and unknown to high. For a subject if a lab is collected multiple times at post baseline, as long as one lab value is low this subject is regarded to have “low” post-baseline for this lab parameter. Similarly, if at least one post-baseline lab value is “high” this subject is regarded to have “high” post-baseline for this lab parameter.

For urinalysis, shifts tables from baseline to high/positive post-baseline will be presented. Shift to high/positive includes low to high/positive, normal/negative to high/positive, or unknown to high/positive.

Markedly abnormal laboratory

Markedly abnormal indicate clinically significant laboratory abnormalities determined by Biogen. For hematology and blood chemistry the number and percentage of subjects with markedly abnormal laboratory post-baseline will be summarized by treatment group from the criteria in Table 7. Shifts tables from baseline to markedly abnormal post-baseline will also be summarized. For a subject if a lab is collected multiple times at post baseline, as long as one lab value is markedly abnormal this subject is counted to be markedly abnormal for this lab parameter.

Subject’s listings will also be presented for all subjects with any markedly abnormal laboratory. In the listings, each subject’s complete history from screening to last study visit for that specific laboratory test meeting the criteria will be listed.

Table 7: Criteria for markedly abnormal laboratory

Parameter name	Unit	Low	High
Hematology			
White blood cells	$\times 10^9$ cells/L	<3.0	>16
Lymphocytes	$\times 10^9$ cells/L	<0.8	>12
Neutrophils	$\times 10^9$ cells/L	<1.5	>13.5
Monocytes	$\times 10^9$ cells/L	N/A	>2.5
Eosinophils	$\times 10^9$ cells/L	N/A	>1.6
Basophils	$\times 10^9$ cells/L	N/A	>1.6

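### SAP 4.5.8 keeps one ECG per window, has no rule for same-day repeats and no summary over all post-baseline ECGs, so an abnormal ECG can be missing from every ECG summary table

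*SAP*

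**What the plan says.** SAP 4.5.8 assigns ECGs to the windows of its Table 12: Week 2, Days 2 to 21 (target 15); Week 4, Days 22 to 35 (target 29); Week 6, Days 36 to 49 (target 43); Week 8, Days 50 to 70 (target 57); Week 12, Day 71 to end of study (target 85). Where a window holds more than one value, "the closest record to the target visit day will be used for the by visit analysis". Where two are equally distant, "then the record with the later date will be used for the by visit analysis". Nothing limits the choice to scheduled ECGs.

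The ECG outputs are descriptive statistics by visit, plots of mean QTcB and QTcF, and a shift table: "a shift table of ECG interpretation results will be presented at each visit by treatment group". There are also listings: "Individual subject listings of ECG parameters at each timepoint will also be provided by treatment group".

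On the protocol side, Table 4, footnote 2 allows visits within 3 "calendar days relative to baseline", and Section 5 lets the investigator add unplanned visits. Section 14.1.6 calls for two confirmatory ECGs, minutes apart, when QTc is at least 45 msec above baseline or at least 500 msec. If the prolongation is confirmed, "then a single ECG must be repeated at least hourly until QTc values from 2 successive ECGs fall below the threshold value". Table 4, footnote 10 adds, at Japanese sites only, an ECG 2 hours postdose on Day 1 and another on Day 8.

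**The concern.** Some of the extra ECGs in this trial are taken because of what an earlier ECG showed. A rule that picks one record per window by calendar distance treats them as interchangeable with the planned ones. If the planned ECG is abnormal and a later one is nearer the target day, the planned one drops out of that visit's mean, plot and shift count.

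Other safety data have a second route into the tables. For laboratory results, SAP 4.5.3.2 counts any post-baseline abnormality: "as long as one lab value is markedly abnormal this subject is counted to be markedly abnormal for this lab parameter". For vital signs, SAP 4.5.4 tabulates the incidence of clinically relevant outliers. The readable ECG section has no equivalent, and protocol 16.4.2 adds no ECG analysis. At stake is whether a reader of the ECG tables sees every subject who had an abnormal ECG or a prolonged QTc on treatment. The protocol treats QTc as a safety matter: it sets QTcF entry limits and QTc levels that trigger repeat recording.

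**Working it through.** The plan states no figure to reproduce. The check applies the SAP 4.5.8 rule to the days the protocol allows.

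**1. Later-day ECGs.** Inputs: Table 12 targets T and the visit tolerance of 3 days. Let the scheduled ECG fall on day S and a follow-up on a later day F in the same window. The follow-up is kept if |F − T| ≤ |S − T|, because a tie goes to the later date.

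- If S = T − e with e = 1, 2 or 3, the condition becomes S < F ≤ T + e, which covers 2e days: 2, 4 or 6.
- If S is on or after T, any later F is further from T, so the scheduled ECG is always kept.

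| Scheduled ECG | Displaced by a follow-up | Week 4 example (target 29) |
|---|---|---|
| 3 days early | 1 to 6 days later | Day 26 by Days 27–32 |
| 2 days early | 1 to 4 days later | Day 27 by Days 28–31 |
| 1 day early | 1 to 2 days later | Day 28 by Days 29–30 |
| On or after target | never | Days 29–32 kept |

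Enumerating all five post-baseline windows gives the same pattern in each.

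**2. Same-day repeats.** The repeats in protocol 14.1.6 are 2 to 4 minutes apart, then at least hourly. Two records on one day have the same distance and the same date, so neither part of the ECG rule separates them. The laboratory section does have a rule for this: "If there are 2 values on the same day for a certain parameter for a subject, then the record with the later time" is used. SAP 4.5.8 does not repeat it.

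**3. Japan-specific ECGs.** With the tolerance, the Day 8 ECG falls on Days 5 to 11. Table 12 has no Week 1 row, so it enters the Week 2 window at a distance of 15 − 11 = 4 to 15 − 5 = 10 days. The Week 2 ECG falls on Days 12 to 18, at a distance of 0 to 3 days, and wins in every combination. The Day 1 postdose ECG fits no window: the baseline row takes pre-dose values and the Week 2 row starts on Day 2.

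**4. Size on a mean.** Assume, for illustration only, one subject at +50 msec on Day 26 and +10 msec on Day 28. Week 4 then uses +10. The arm mean changes by (50 − 10)/73 = 0.55 msec with 73 subjects, or 40/51 = 0.78 msec with the 51 evaluable subjects of the sample size calculation.

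**The case against.** Several objections are sound and limit the point.

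- **Two kinds of extra ECG.** The repeats that the protocol orders fall within minutes to hours, whereas displacement needs an ECG on a later day. The protocol allows such an ECG but does not require it.
- **Last repeat wins.** A reader might infer that the final, recovered repeat replaces the prolonged reading. The documents do not say so. The later-time rule is stated for laboratory data only, and for ECGs the choice is simply unspecified. Nor is recovery assured: protocol 14.1.6 also provides for continuous monitoring after 4 hours and a cardiologist consultation after 8.
- **Systematic bias toward normal.** The rule does not look at results. A normal Day 26 ECG followed by an abnormal unplanned one on Day 28 is tabulated as abnormal. A net pull toward normal is plausible, because follow-up tends to be prompted by abnormal findings, but it is not shown.
- **A lost abnormal shift.** The example in step 4 does not imply that a shift count falls from one to zero. The table shifts ECG interpretation, not QTc change. A rise from 380 to 430 msec is +50 msec yet stays under the protocol's QTcF entry limits of 450 and 470 msec.
- **Survival only in a listing.** Under protocol 15.1.1 an ECG result that is clinically significant, needs corrective therapy or is serious is an adverse event, and SAP 4.5.2.1 tabulates those by arm.
- **A uniform convention.** Choosing the record nearest the target, with ties to the later one, is also the SAP's rule for efficacy, laboratory and vital-sign data.

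The last objection does not settle the matter, because laboratory and vital-sign data have a further summary that can catch what a by-visit rule leaves out. The readable ECG plan has none.

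**Conclusion.** The point holds in limited form. An abnormal post-baseline ECG can be absent from every ECG summary table in three ways: a scheduled ECG done 1 to 3 days early is displaced by a later unscheduled one; an undefined choice is made among same-day repeats; or the record is a Japan-specific Day 1 postdose ECG, or a Day 8 ECG when a Week 2 ECG exists. It remains in the listings and, if clinically significant, in the adverse event tables.

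The effect on means is small and its direction uncertain. The larger weakness is in counting affected subjects by arm. How often this would occur cannot be derived from the documents, because it depends on how many visits run early and how many extra ECGs are taken. The conclusion covers the readable text only, since parts of the SAP after 4.5.9 are blacked out. It does not touch the efficacy analysis.

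**What to change.** Amend SAP 4.5.8 before unblinding:

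1. For by-visit statistics, plots and shifts, use the scheduled ECG of that visit. Use an unscheduled or triggered repeat only if the scheduled one is missing or technically invalid (protocol 14.1.6 mentions lead misplacement), and state which record is taken when several fall on the same day. Only the screening and Day 1 ECGs are planned in triplicate, so no averaging rule is needed for post-baseline scheduled ECGs.
2. Add by-arm summaries over all valid post-baseline ECGs, including repeats, unscheduled and Japan-specific ones: (a) a shift from baseline to worst ECG interpretation; (b) the number of subjects with any QTcF value at least 45 msec above baseline, and the number with any value of at least 500 msec. These thresholds already stand in protocol 14.1.6, which defines baseline QTc as the mean of the Day 1 predose triplicate. Part (b) is needed because a worst-interpretation table can miss a large QTc rise that is read as normal.

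The cost is SAP wording and one or two tables from data already collected, with no change to trial conduct. One drawback is that subjects with more ECGs have more chances to be counted, which is already true of the laboratory tables and can be noted in a footnote.
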